4.5.10.1 Composite Unified Huntington's Disease Rating Scale

The cUHDRS is a composite motor, cognitive, and global functional clinical outcome measure in patients with HD comprised of an equally weighted sum of Z scores of the TFC, the TMS, the SDMT, and the SWR scores from the UHDRS (Huntington Study Group 1996). It is a multidomain measure of clinical decline that tracks underlying progressive brain changes and is related to changes in daily functional ability (Schobel et al. 2017).

The formula for cUHDRS scoring was originally developed for use in HD Stages 1 and 2 (TFC 7–13) but has since been updated to encompass early HD Stage 3. This led to an update to the reference population (using ENROLL-HD data) from TFC=7–13 to TFC=5–13 (in both cases, a lower age cutoff of 20 years was used to limit the number of individuals included with juvenile-onset HD). The cUHDRS is scored using the following formula:

$$\text{cUHDRS} = \left(\frac{\text{TFC} - 8.8}{2.8} \right) - \left(\frac{\text{TMS} - 34.4}{17.4} \right) + \left(\frac{\text{SDMT} - 25.2}{12.4} \right) + \left(\frac{\text{SWRT} - 58}{21.2} \right) + 10.0$$

4.5.10.2 Total Functional Capacity Scale

The TFC is a validated measure of global patient function in HD. The TFC represents the investigator's assessment of the patient's capacity to perform a range of activities of basic daily living, including working, chores, managing finances, eating, dressing, and bathing. The 5-item assessment is based on a brief interview with the patient. The TFC score ranges from 0–13, with a higher score representing better functioning. A 1-point change in TFC score is a clinically meaningful change in patient function (e.g., a 1-point decline may indicate the loss of ability to work in a normal capacity) (Huntington Study Group 1996). The TFC takes approximately 10 minutes to administer and will be completed at specified clinic visits.

4.5.10.3 Total Motor Score

The TMS is a holistic measure of motor function in HD that is linked to both functional capacity based on the TFC score, independence, and driving status (Beglinger et al. 2012; Schobel et al. 2017).

The TMS score is the sum of the individual motor ratings obtained from administration of the 31-item motor assessment portion of the UHDRS by the investigator. The score ranges from 0–124, with a higher score representing more severe impairment. The TMS takes approximately 15 minutes to administer and will be completed at clinic specified visits.

4.5.10.4 Symbol Digit Modalities Test

The SDMT is used to assess attention, visuoperceptual processing, working memory, and psychomotor speed. It has been shown to have strong reliability and validity (Smith 1982). The patient pairs abstract symbols with specific numbers according to a

translation key. The test measures the number of items correctly paired (maximum of 110 correct pairs) in 90 seconds. The SDMT will be administered at specified clinic visits and can be completed in less than 5 minutes. It will also be administered at specified timepoints on the Roche HD mobile app (via electronic SDMT) in patients issued with devices.

4.5.10.5 Stroop Word Reading Test

The SWR Test is a measure of attention, processing, and psychomotor speed and depends upon quick verbal motor output. Patients are presented with a page of color names (i.e., "BLUE," "RED," or "GREEN") printed in black ink and are asked to read aloud as many words as possible within a given amount of time (in 45 seconds). The number of words read correctly is counted, with a higher score indicating better cognitive performance. It will also be administered at specified timepoints on the Roche HD mobile app (via electronic SWR) in patients issued with devices.

4.5.10.6 Independence Scale

A patient's IS score is a measure of disease progression in functional disability and will be completed to evaluate a patient's degree of independence at screening. It is a subscale of the UHDRS. The scale consists of 19 discrete levels ranging from 10–100 (by 5), in which a score of 100 indicates no special care is needed and a score of 10 indicates the patient is fed by tube and requires total bedcare. This scale will only be performed for patients who were screened and eligible for Study BN40423 but could not be randomized due to challenges relating to the COVID-19 pandemic.

4.5.10.7 Huntington's Disease Daily Activities Scale

The HD-DAS assesses patients' daily function. Following a semi-structured interview with the patient, the patient's ability level to perform daily tasks such as eating or using a telephone will be recorded. Each item is scored on a 4-point Likert-type scale, where 0 indicates no impact and 3 indicates severe impact. The HD-DAS can be completed in approximately 25 minutes.

4.5.10.8 Clinical Global Impression, Severity and Change Scales

The CGI-S is a single-item measure of current global severity and is completed by the clinician at specified clinic visits. The CGI-S is assessed using an 11-point numeric rating scale, where higher scores indicate greater severity. The CGI-S can be completed in approximately 2 minutes.

The CGI-C is a single-item measure of change in global status (since starting the study) and is completed by the clinician at specified post-baseline visits. The CGI-C has seven response options: "very much worse," "much worse," "minimally worse," "no change," "minimally improved," "much improved," and "very much improved." The CGI-C can be completed in approximately 2 minutes. To assess the relevance of this change, a follow-up question with dichotomous response options ("yes" or "no") asks if the change has had a meaningful impact on the patient's well-being.

4.5.10.9 Montreal Cognitive Assessment

The MoCA is a patient-completed assessment used to detect cognitive impairment. It contains a series of basic assessments, including attention and visuospatial tasks. The total score ranges from 0–30, where lower scores indicate greater impairment. The MoCA will be used in this study to assess cognitive status at regular intervals throughout the study and takes approximately 10 minutes to administer.

4.5.10.10 Columbia-Suicide Severity Rating Scale

The C-SSRS is a structured tool to assess suicidal ideation and behavior. Four constructs are measured: severity of ideation, intensity of ideation, behavior, and lethality of actual suicide attempts. Binary (yes/no) data are collected for 10 categories, and composite endpoints based on the categories are followed over time to monitor patient safety (Posner et al. 2011). It maps to the Columbia-Classification Algorithm for Suicide Assessment and meets the criteria listed in the U.S. Food and Drug Administration (FDA) draft guidance for assessment of suicidality in clinical trials (FDA 2012). The C-SSRS will be used to assess eligibility for the study for patients required to undergo screening (full version at screening, requiring approximately 20 minutes to administer) and to monitor patients throughout the study at clinic visits (follow-up version, requiring approximately 5 minutes to administer, assuming absence of suicidal ideation and no change in clinical status from previous administration).

The patient should be referred for immediate psychiatric evaluation in any event of suspected active suicidal intent, significant suicidal behavior, or clinical finding suggesting that the patient is dangerous to himself or herself.

4.5.10.11 EuroQol 5-Dimension, 5-Level Questionnaire

The EQ-5D-5L is a validated self-report health status questionnaire used to calculate a health status utility score for use in health economic analyses (EuroQol Group 1990; Brooks 1996; Herdman et al. 2011; Janssen et al. 2013). There are two components to the EQ-5D-5L: a 5-item health state profile that assesses mobility, self-care, usual activities, pain/discomfort, and anxiety/depression, as well as a VAS that measures health state. Published weighting systems allow for creation of a single composite score of the patient's health status (Index score) from the 5-item scores (i.e., does not include the VAS). The EQ-5D-5L takes approximately 5 minutes to complete. The Index score will be used in this study for informing pharmacoeconomic evaluations. The VAS score will be used to assess health-related quality of life (HRQoL). The EQ-5D-5L will be completed by the patient at study drug administration visits on an electronic device. In addition, it will be completed remotely by the patient on the Roche HD mobile app.

4.5.10.12 Roche HD Mobile Application: Remote Testing (Smartphone and Wrist-Worn Wearable)

Smartphones and wrist-worn wearables have high-quality sensors that enable the remote, non-invasive, frequent, and precise measurement of motor and non-motor symptoms (Maetzler et al. 2013; Andrzejewski et al. 2016; Adams et al. 2017;

Lipsmeier et al. 2018). If a patient already has a preconfigured smartphone and wrist-worn wearable with installed software for the Roche HD mobile app assessments from the preceding study, they will continue to use those devices in this study. Although the majority of assessments on the Roche HD mobile app are consistent across the preceding studies, some of the PROs will differ. Patients will continue to complete the PROs from the preceding study, thus not all patients will complete all PROs (e.g., the WHODAS 2.0 will not be completed by patients previously in Study BN40423). Details of remote assessments are contained in [Appendix 7](#). If patients did not have a preconfigured smartphone and wrist-worn wearable in the preceding study, they will not be provided devices in this study. Patients screened in Study BN40423 but not randomized due to logistical challenges resulting from COVID-19 will be provided with a smartphone and wrist-worn wearable. The devices and software will monitor motor symptoms, non-motor symptoms, and activities associated with routine daily living throughout the course of the study. Additional details are available in the Roche HD mobile app (smartphone) manual.

Patients will be asked to complete an "active test" every day at approximately the same time (ideally in the morning, after breakfast). The active test consists of a short, preconfigured schedule of tasks that assess motor symptoms (upper and lower body movements, upper limb dexterity, and voice) and non-motor symptoms (processing speed, voice). These tasks are described in [Appendix 9](#). Testing will last approximately 5–10 minutes in total on a typical day of testing. Not all tests are daily. Additional information on the approach, tasks, and schedule are available in the Roche HD mobile app manual.

For "passive monitoring," patients will be instructed to carry the smartphone in a manner convenient to them (e.g., in a pocket or in a Sponsor-provided pouch) and wear the wrist-worn wearable throughout the day as they go about their daily routines.

Patients will be encouraged to adhere to the daily schedule of tasks as much as possible; however, patients will not be excluded from the study for poor adherence nor will missing a daily test be considered a protocol deviation. Device sensor data will be recorded continuously, throughout the active tests and passive monitoring. Sound will only be recorded during selected active test tasks. Data will be encrypted and uploaded to secure servers when the smartphone is connected to Wifi. Patients will be asked to charge the devices overnight. If patients have a Wifi network at home, they will be encouraged to connect their smartphone to enable data transfer. If no Wifi network is available, the sensor data will be transferred during clinic visits or after the devices have been returned.

Devices may reach the end of their lifespan or be broken during this study. In those cases, they may be replaced upon discussion on a case-by-case basis.

During the course of this study (ca. 2022), the Roche HD mobile app may be available for download by study participants with compatible smartphones. All patients, will have the option to download the app on their personal smartphones and continue (or restart) with the Roche HD mobile app assessments and passive monitoring. If patients download the app on their personal smartphone, they should return the provisioned devices.

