2.2 EXPLORATORY EFFICACY OBJECTIVES

The exploratory efficacy objective for this study is to evaluate the efficacy of RO7234292 on the basis of the following endpoints:

- Change from baseline in the composite Unified Huntington's Disease Rating Scale (cUHDRS) score as assessed Q16W
- Change from baseline in scores for the following individual scales as assessed Q16W:
 - Total Functional Capacity Scale.
 - Total Motor Score (TMS).
 - Symbol Digit Modalities Test (SDMT).
 - Stroop Word Reading (SWR) test.

- Change from baseline in the Clinical Global Impression, Severity Scale (CGI-S) score as assessed Q16W
- Proportion of patients with an unchanged or improved score on the Clinical Global Impression, Change Scale (CGI-C) score from baseline as assessed Q16W
- Change from baseline in the Huntington's Disease Daily Activities Scale (HD-DAS) score as assessed Q16W
- Change from baseline in the sensor-based measures collected by the Roche HD mobile application (app; smartphone and wrist-worn wearable) as assessed Q16W

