Appendix 9: Roche HD Mobile Application: Active Test (cont.)

Speeded Tapping Test

The Speeded Tapping Test asks participants to tap the smartphone screen as fast and regularly as possible, using the index finger of both the left and right hands. The test assesses bradykinesia. Performance will also be impacted by chorea and dystonia. It is modeled on tapping tests shown to be sensitive to symptom changes in early HD (Bechtel et al. 2010; Tabrizi et al. 2012). A similar finger tapping task is also included as part of the UHDRS assessment (Huntington's Study Group 1996).

Draw a Shape Test

The Draw a Shape Test asks participants to trace a series of increasingly complex shapes on the smartphone screen. The shapes include lines, a square, a circle, an eight, and a spiral. This test is designed to assess visuomotor coordination and fine motor impairment in patients with early HD. It is modeled on circle tracing tasks that have been shown to be sensitive to symptom changes in early HD (Say et al. 2011; Tabrizi et al. 2013).

Chorea Test

The Chorea Test asks participants to hold the smartphone still in their hand with their arm outstretched, and wear the wrist-worn wearable. As a dual task, participants will also need to count backwards aloud. To ensure correct execution, voice will be recorded. The test is designed to assess chorea. It draws on other sensor-based approaches to measure chorea (Reilmann et al. 2010, 2011; Kegelmeyer et al. 2017). A chorea assessment is also part of the UHDRS (Huntington's Study Group 1996).

Balance Test

The Balance Test asks participants to stand still while wearing the smartphone and wrist-worn wearable. It is an assessment for patients' static balance function. Sensor-based approaches for measuring static balance have been shown to be sensitive to differences in symptoms in early HD (Dalton et al. 2013). The test is also part of established scales like the Berg Balance Scale (Berg et al. 1992), which are used in HD (Busse et al. 2009; Rao et al. 2009). The test is anchored to the UHDRS assessments for maximal dystonia, maximal chorea, and tandem walking (Huntington Study Group 1996).

U-Turn Test

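### Patients who move the app to a personal phone are told to return devices that appear to include the wearable the sensor endpoint needs, and no rule covers mixed hardware

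*Combined protocol and SAP*

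**What the plan says.** **Endpoint.** Section 2.2 lists, among the exploratory efficacy endpoints, "Change from baseline in the sensor-based measures collected by the Roche HD mobile application (app; smartphone and wrist-worn wearable) as assessed Q16W".

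**Baseline hardware.** Under Section 4.5.10.12, patients who had a preconfigured phone and wearable in the preceding study carry them over. The group that was screened for BN40423 but not randomized because of COVID-19 is supplied with both. Other patients without devices are not given any. Appendix 1a (footnote x) keeps the same devices where possible.

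**The switch.** The same section says that "the Roche HD mobile app may be available for download by study participants with compatible smartphones". It continues: "All patients, will have the option to download the app on their personal smartphones", and they may then "continue (or restart) with the Roche HD mobile app assessments and passive monitoring". It adds: "If patients download the app on their personal smartphone, they should return the provisioned devices".

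**Where the wearable is used.** Passive monitoring has patients wear it through the day (Section 4.5.10.12). Section 4.5.10.12.1 has patients bring both phone and wearable to every clinic visit. In Appendix 9 the Chorea Test asks patients to "hold the smartphone still in their hand with their arm outstretched, and wear the wrist-worn wearable", and the Balance and U-Turn tests are also done with it on.

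**Analysis.** Section 6.6 plans summary tables by arm and assessment time, in absolute values and change from baseline. Any modelling is left to a later SAP.

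**The concern.** A change-from-baseline measure assumes that the same thing is measured at both ends. Here the instrument may change between baseline and follow-up in two ways. The phone is replaced by a patient's own model, with its own sensors and screen, which could matter for tapping and drawing tasks. The wearable, if it goes back with the phone, is no longer there for the measures that use it.

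The plan takes more care elsewhere. Section 4.5.9 asks for the same ECG machine whenever possible, and Section 3.3.2.3 keeps MRI measures consistent with the preceding study. For the sensor data, the visible text has no device variable, no overlap period and no rule for values recorded after a switch. At stake is whether the by-visit sensor summaries can be read as disease change rather than as a mixture of disease change and change of hardware.

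**Working it through.** The plan states no figure for this point, so the check sets its sections side by side.

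1. **What is to be returned.** The return sentence in Section 4.5.10.12 speaks of provisioned devices in the plural and does not name the wearable. Earlier text in the same section describes the supplied set as a phone and a wearable. No text lets a switcher keep the wearable or names a substitute. Return of the wearable is therefore an inference, but the natural one.

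2. **What still needs it.** The endpoint definition names the wearable. Section 4.5.10.12 lets switchers go on with passive monitoring, which it describes with the wearable worn. Section 4.5.10.12.1 makes no exception for switchers when it asks for the wearable at every clinic visit. If the wearable has gone back, none of these can be followed as written.

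3. **Which tasks are touched.** Appendix 9 has eight performance tasks.
   - Three name the wearable: Chorea, Balance and U-Turn. They face a change of phone and possible loss of the wearable.
   - Five do not: electronic SDMT, electronic word reading, Speeded Tapping, Draw a Shape and Walk. They face the change of phone only.

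4. **What the tables would contain.** Section 6.6 groups by arm and assessment time. Nothing in it separates values by device, re-baselines at a switch or stops at a switch. Section 7.4 holds the efficacy analysis of these data to study end, unless they are chosen for a pre-specified interim, so a final analysis could include post-switch values.

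5. **How an offset would act (illustration only; all inputs assumed).** Let p be the share of patients in a visit summary who have switched, and d the average hardware offset in SD units.
   - Shift in an arm's mean change = p × d. At the low end, 0.10 × 0.2 = 0.02 SD. At the high end, 0.50 × 0.5 = 0.25 SD.
   - Shift in a between-arm difference, with the same offset in both arms = (p in Q8W − p in Q16W) × d. This is zero if the arms switch equally.

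   Both formulas need an offset with a common direction. Offsets that differ in sign between phone models would partly cancel in the mean and add spread instead.

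6. **Patients who start on a personal phone.** A patient never given devices who first uses the app after its release has no sensor value at inclusion. No change from baseline can be computed, so such a patient adds no offset to the change summaries.

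**The case against.** The strongest reply is that the option preserves data. The study is expected to last about six years, devices wear out and are replaced only case by case, and a personal phone may keep a series going that would otherwise end. The endpoint is exploratory and descriptive, and Section 5.3.5.13 excludes wearable data from the safety analyses. The app manual and the later SAP, neither of which is available here, may already contain handling rules. Section 7.4 gives the sponsor responsibility for the integrity and quality of sensor data and says that technical status is logged. All of this stands, and it limits the weight of the point. It does not remove the conflict within the protocol over the wearable.

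Four stronger readings are tempting, and the documents do not support them.

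- **That return is compulsory and wearable data are wholly lost in switchers.** The text says should. Compulsory return, in Section 4.5.10.12.1, is tied to ineligibility, end of study or early termination. Loss of the wearable follows only by inference, and the instruction to bring it to every visit points the other way.
- **That a device shift will pass for an off-drug change, because 2022 falls after the dosing pause of 22 March 2021.** While the pause lasts, post-switch values would indeed be off-drug values. But release in about 2022 is only possible, each patient chooses whether and when to move, and the tables run by assessment time rather than calendar date. No on-drug versus off-drug sensor comparison is specified.
- **That a particular bias has been shown.** The documents contain neither a switching share nor an offset.
- **That the main summary must be confined to baseline devices.** That gives up follow-up, possibly selectively. A sensitivity analysis answers the question at lower cost.

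**Conclusion.** The point holds as an internal conflict with a gap in data handling. The return instruction in Section 4.5.10.12, read with that section's description of the devices, takes away hardware on which Section 2.2, passive monitoring, Section 4.5.10.12.1 and three of eight Appendix 9 tasks depend. For patients who switch, phone-based change from baseline would also mix hardware in the planned tables. Mixing is permitted rather than certain: it depends on app release, a compatible phone and the patient's choice. The size of any device effect cannot be derived from the documents. The 0.02 to 0.25 SD range above shows only how assumed inputs would act. No safety conclusion is touched, so this is a minor point, worth correcting because the correction is cheap and phone details not recorded at the time of a switch may be unrecoverable later.

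**What to change.** - **Section 4.5.10.12:** state that patients who move to a personal phone return only the provisioned phone and keep the wearable until end of study. Reconcile this with Sections 2.2 and 4.5.10.12.1. Whether the wearable works with a personal phone is not stated. If it does not, say that wearable-based measures are missing from the switch onward.
- **Data collection:** record phone model and the date of any switch or replacement.
- **Analysis text (Section 6.6 or the SAP):** report the sensor change-from-baseline summaries with post-switch data flagged, and add a sensitivity analysis limited to data from the device set used at baseline. Exclude from change-from-baseline summaries patients whose first sensor data in this study come from a personal phone.

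The cost is a short protocol amendment, one extra data field, one extra set of tables and wearables out with patients for longer. The sensitivity analysis will rest on fewer patients at later visits, and those who keep their original devices may differ from those who switch, so it should be read beside the full summary and not in place of it.
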